**CONFIDENTIAL**

CCI

[figure not shown]
**CONFIDENTIAL**

CCI

[figure not shown]
**CONFIDENTIAL**

CCI

[figure not shown]

**CONFIDENTIAL**

[figure not shown]
CCI

CCI - This section contained Clinical Outcome Assessment data collection questionnaires or indices, which are protected by third party copyright laws and therefore have been excluded.

CCI

**CONFIDENTIAL**

CCI

[figure not shown]

CCI - This section contained Clinical Outcome Assessment data collection questionnaires or indices, which are protected by third party copyright laws and therefore have been excluded.

[figure not shown]
**CONFIDENTIAL**

CCI

[figure not shown]
**CONFIDENTIAL**

CCI

[figure not shown]
CONFIDENTIAL

CCI

[figure not shown]
**CONFIDENTIAL**

CCI

**CONFIDENTIAL**

CCI

## **4.5. Safety Analyses**

The safety analyses will be based on the Safety analysis set, unless otherwise specified.

### **4.5.1. Extent of Exposure**

Study treatment is administered (subcutaneously injected) approximately every 4 weeks and each dose viewed as providing therapeutic coverage for 4 weeks (28 days).

Duration of exposure is calculated based on the therapeutic coverage as follows:

- Duration (days) =  
(Last IP Administration Date – First IP Administration Date + 29)
- Duration (months) =  
(Last IP Administration Date – First IP Administration Date + 29)\*12/365.25
- Participant-years exposure =  
(Last IP Administration Date – First IP Administration Date + 29)/365.25

The extent of exposure to study treatment (mepolizumab/placebo) will be reported, including descriptive statistics of duration of exposure in addition to the number and percentage of participants exposed for  $\geq 1 < 3$ ,  $\geq 3 < 6$ ,  $\geq 6 < 9$ ,  $\geq 9 < 12$  and  $\geq 12$  months, based on each participant's duration of exposure rounded to the nearest whole month. The number of treatments administered and total participant-years exposure will also be summarised.

#### **4.5.1.1. Self-administration of Study Treatment**

A subset of Japanese participants who are willing can self-administer study treatment under observation of the principal investigator or delegate from Week 32 onwards.

A self-administered injection is considered successful if the following criteria are met:

- Use of a correct injection site (abdomen or thigh)
- Full dose administered: participant fully inserts the needle, slowly presses the plunger until the stopper reaches the bottom of the syringe and activates the needle guard by moving the thumb up

If the above criteria are met, the investigator will confirm the injection was successfully delivered.

The number and proportion of participants with at least one successful self-administered injection and the number and proportion of participants with all self-administered injections successfully delivered will be summarised. Participants with at least one unsuccessful self-administered injection and reasons for the unsuccessful delivery of study treatment will be listed.

#### **4.5.2. Adverse Events**

Adverse events analyses including the analysis of adverse events (AEs), Serious AEs (SAEs) and other significant AEs will be based on GSK Core Data Standards.

Adverse events will be coded using the standard Medical Dictionary for Regulatory Affairs (MedDRA dictionary), with the maximum severity of each AE determined by the investigator (as mild, moderate or severe).

An overview summary of AEs, including counts and percentages of participants with any AE, AEs related to study treatment, AEs leading to permanent discontinuation of study treatment, AEs leading to withdrawal from the study, AEs leading to dose delays, SAEs, SAEs related to study treatment, fatal SAEs, and fatal SAEs related to study treatment will be produced.

AEs will be considered on-treatment for at least 4 weeks (28 days) following the last dose of study treatment. AEs which occur more than 28 days following the last dose of study treatment will be considered as post-treatment. The number and percentage of participants experiencing at least one AE during the on-treatment and post-treatment periods will be summarised separately. Additionally, summaries of the number and percentage of participants with any on-treatment AEs by maximum severity will be produced. If an adverse event severity is missing, the severity is to be populated as 'UNKNOWN'.

The frequency and percentage of AEs will be summarized and displayed in two ways: 1) in descending order by SOC and PT and 2) in descending order by PT only.

Common AEs, defined as  $\geq 3\%$  (prior to rounding) in any treatment group, will be reported. The summary table will be displayed by PT only.

A separate summary will be provided for study treatment-related AEs. A study treatment-related AE is defined as an AE for which the investigator classifies the possible relationship to study treatment as "Yes". A worst-case scenario approach will be taken to handle missing relatedness data, i.e. the summary table will include events with the relationship to study treatment as 'Yes' or missing. The summary table will be displayed by SOC and PT.

All SAEs during the on-treatment and post-treatment periods will be tabulated based on the number and percentage of participants who experienced an event within each period. In addition, fatal and non-fatal SAEs will be reported separately.

Separate summaries will also be provided for study treatment-related SAEs. A study treatment-related SAE is defined as an SAE for which the investigator classifies the relationship to study treatment as "Yes". A worst-case scenario approach will be taken to handle missing data, i.e. the summary table will include events with the relationship to study treatment as 'Yes' or missing. The summary tables will be displayed by SOC and PT.

AEs leading to discontinuation of study treatment, AEs leading to withdrawal from the study and AEs reported on the day of dosing with study treatment will be both summarised. The summary tables will be displayed by SOC and PT.

Additional summaries of on-treatment AEs by time to onset (0-<12 weeks, 12-<24 weeks, 24-<36 weeks, 36-<48 weeks and  $\geq$ 48 weeks) and on-treatment AEs in participants who have at least one anti-drug antibody (ADA) positive result and those with all negative ADA results post-baseline will be reported.

AEs and SAE summaries will also be presented by Background INCS use subgroup (defined within Section 4.11.1).

The incidence of AEs and SAEs (Fatal and Non-Fatal) of COVID-19, COVID-19 AEs leading to study drug discontinuation, COVID-19 AEs leading to study withdrawal, and COVID-19 AEs by maximum severity, will be obtained from the standard AE and SAE summaries.

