1.2. Schema

1.3. Schedule of Activities (SoA)

	Procedure	Pre-screening ¹	Screening ¹	Treatment															
				0	1	2	3	4	5	6	7	8	9	9a	10	11	12	13	14
Visit		0	up to 28 ±7 days prior to Day 1	1	29	57	85	113	141	169	197	204 (±1day)	225	253	281	309	337	365	28 ±7 days post last dose
Study Day (visit window ±7 days)				0	4	8	12	16	20	24	28	29	32	36	40	44	48	52	
Week																			
Screening/baseline	Informed consent	X																	
	Blood collection for eosinophils eligibility confirmation (if required) ²	X																	
	Inclusion and exclusion criteria		X																
	Demography		X																
	Full physical exam including height and weight		X																
	Medical history (includes substance usage and family history of premature CV disease CRSwNP/ECRS and asthma therapy, asthma and exacerbation history and concomitant medications)			X															
	SAE Review			X															
	History of HIV and Hep B, Hep C screen				X														
	Past and current medical conditions including cardiovascular medical history					X													
	History of systemic CS use for NP					X													
	History of NP surgery						X												

	Procedure	Pre-screening ¹	Screening ¹	Treatment																	
				0	1	2	3	4	5	6	7	8	9	9a	10	11	12	13	14	15	
Visit	Study Day (visit window ± 7 days)		up to 28 ± 7 days prior to Day 1	0	1	2	3	4	5	6	7	8	9	9a	10	11	12	13	14	15	IP DISC / EW Visit
Study Day (visit window ± 7 days)						1	29	57	85	113	141	169	197	204 (± 1 day)	225	253	281	309	337	365	28 ± 7 days post last dose
Week						0	4	8	12	16	20	24	28	29	32	36	40	44	48	52	
	Parasitic screening ³					X															
	Screening 12-lead ECG					X															
	Screening Vital signs					X															
	Assessment of endoscopic NP score ¹¹					X															
	Assessment of VAS for NP symptoms including Overall VAS ⁶					X															
	Assessment of Screening CT ⁴					X															
	Screening Laboratory assessments: Haematology (including blood eosinophils) and chemistry (including liver chemistries)					X															
	Screening Urinalysis					X															
	Urine pregnancy test (WOCBP only) ⁵					X															
	Dispense and Train in the use of eDiary ⁶					X															
	Register visit	X	X	X	X	X	X	X	X	X	X	X	X		X	X	X	X	X	X	
	Randomisation					X															
	Genetics sample ⁷														X						
Efficacy	Assessment of NP Surgery					X	X	X	X	X	X	X	X		X	X	X	X	X	X	

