4.4. End of Study Definition

A participant is considered to have completed study treatment if he/she receives study treatment at Visit 14 (Week 48). A participant is considered to have completed the study if he/she has completed all phases of the study including the last visit (Visit 15/Week 52) or the last scheduled procedure shown in the SoA, (Section [1.3](#)) whichever is earlier.

The end of the study is defined as the date of the last visit of the last participant in the study or last scheduled procedure shown in the SoA for the last participant in the trial globally, whichever is earlier.

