6.1. Study Intervention(s) Administered

Study intervention or treatment is defined as any investigational treatment(s), marketed product(s), placebo, or medical device(s) intended to be administered to a study participant according to the study protocol.

A liquid formulation of mepolizumab will be provided as pre-filled syringes in a safety syringe device (SSD) for this study. The liquid formulation has a distinct advantage over the lyophilised product as it does not require reconstitution, and the devices (upon commercial registration) will simplify and facilitate administration.

There will also be a matched safety syringe with placebo. Both active and placebo drug products are stored at 2-8°C condition, protected from light.

The study consists of up to 17 visits with a maximal total treatment duration of approximately 52 weeks and maximum study duration of approximately 56 weeks. Screened participants will enter a 4 weeks run-in period, followed by up to 52 weeks double-blind treatment period.

Participants who are successfully enrolled into the study will be randomised in a 1:1 ratio into one of two treatment groups, receiving a total of thirteen doses (one every four weeks):

- Group 1: 100 mg SC of mepolizumab on top of SoC
- Group 2: Placebo SC on top of SoC

The end of study assessments for each individual participant will be performed at Visit 15 (Week 52), 4 weeks following the last dose of IP.

Study Treatment	
Product name:	Mepolizumab Injection, 100 mg/mL
Device:	Safety syringe
Formulation description:	100 mg/mL mepolizumab with sodium phosphate, citric acid, sucrose, Disodium EDTA, Water for Injection and polysorbate 80
Dosage form:	Sterile, liquid formulation
Unit dose strength(s)/Dosage level(s):	100 mg/mL; 1.0 mL (deliverable)
Route of Administration	SC injection
Dosing instructions for HCP:	SC dose in thigh, abdomen or upper arm every 4 weeks
Dosing instruction for self-injection:	SC dose in thigh or abdomen every 4 weeks
Physical description: mepolizumab	Clear to opalescent, colourless to pale yellow to pale brown sterile solution for SC injection in a single-use, safety syringe
Physical description of injection device:	Single use, disposable safety syringe device assembled with a pre-filled syringe containing mepolizumab solution. A plastic needle cover shields the needle before and after injection to minimise the potential for needle stick injuries.

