ALP  $< 2 \times$  ULN/missing means it is satisfied unless the ALP is  $\geq 2 \times$  ULN at the time of bilirubin elevation (within 28 days following the ALT elevation). The summary will be produced for worst-case post-baseline only. A listing will be generated of all chemistry and liver function tests in participants who met the protocol defined liver stopping or liver monitoring criteria.

An e-DISH plot of maximum post-baseline total bilirubin versus maximum post-baseline ALT will be created.

Additionally, the worst-case urinalysis results post-baseline (including both on-treatment and post-treatment data) relative to baseline will be reported. The percentages are based on the number of participants in each treatment group with data for a given test post-baseline. Participants with a missing baseline value are to be assumed to have a negative baseline value.

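### Post-treatment AE and SAE percentages depend on how many participants stop in each arm and how long they are followed, and no post-treatment follow-up time is planned to show this

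*SAP*

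**What the plan says.** **Cut-off and display (SAP 4.5.2).** "AEs which occur more than 28 days following the last dose of study treatment will be considered as post-treatment". For AEs, "The number and percentage of participants experiencing at least one AE during the on-treatment and post-treatment periods will be summarised separately". SAEs are to be "tabulated based on the number and percentage of participants who experienced an event within each period". Neither sentence names a denominator for the post-treatment period.

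**Analysis set (SAP 4.5).** "The safety analyses will be based on the Safety analysis set, unless otherwise specified". The Safety set is everyone randomised who received at least one dose (SAP 3). Nothing in SAP 4.5.2 narrows it for the post-treatment tables. By contrast, SAP 4.5.3.1 states a denominator for urinalysis: "The percentages are based on the number of participants in each treatment group with data for a given test post-baseline".

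**Schedule.** Under Protocol 4.4, "A participant is considered to have completed study treatment if he/she receives study treatment at Visit 14 (Week 48"). Protocol 6.1 has the end-of-study assessments "performed at Visit 15 (Week 52), 4 weeks following the last dose of IP". The Schedule of Activities puts Visit 14 at Day 337 and Visit 15 at Day 365, under a row labelled "Study Day (visit window ±7 days"). AEs are collected until the end of the study (Protocol 8.4.1).

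**Early stoppers.** Protocol 7.1.1 asks that they be followed, where possible, through the Week 52 assessments.

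**Follow-up time.** SAP 4.5.1 defines participant-years for treatment exposure only.

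**The concern.** The post-treatment period begins where a completer's participation nominally ends. A completer can hardly contribute a post-treatment event, while a participant who stops early can be observed off treatment for months. A percentage over everyone dosed puts both in the denominator as if they had the same opportunity.

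This has two consequences. The percentage understates how often AEs occur among those actually observed off treatment. If one arm has more early stoppers than the other, or follows them longer, the arms will also show different percentages even when the AE rate is the same. Without follow-up time beside the percentages, a reader of the clinical study report cannot tell this from a drug effect. At stake is the reading of one set of descriptive safety tables, SAEs included.

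**Working it through.** **1. The plan's own interval.** Day 365 − Day 337 = 28 days, matching the stated 4 weeks. The SAP 4.5.1 exposure formula gives a completer 337 − 1 + 29 = 365 days. On the nominal schedule, post-treatment time is therefore 28 − 28 = 0 days.

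**2. Effect of the visit windows.** With ±7 days on each visit, the gap from Visit 14 to Visit 15 runs from 14 to 42 days, so a completer has at most 42 − 28 = 14 post-treatment days. The share of completers with none depends on how the windows are used:
- 100% if all visits fall on the nominal day
- 63% if half do
- 54% to 59% if visits cluster around it
- 53% if they are spread evenly

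**3. Early stoppers followed to Day 365.** Post-treatment days = 365 − (last dose day + 28). For last doses 1 to 12 (Days 1, 29, …, 309) this is 336, 308, …, 28. If last doses are spread evenly, the mean is 182 days.

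**4. Illustration.** These inputs are assumptions, not document figures:
- AE rate of 1 per participant-year in both arms
- 80 dosed per arm
- every stopper followed to Day 365, with last doses spread evenly
- completer gap uniform on 21 to 35 days, so 7/15 have at least one post-treatment day and the mean is 1.87 days

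The chance of at least one AE is 1 − exp(−days/365.25). Averaged, this is 0.371 for a stopper and 0.0051 for a completer.

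| | 4 of 80 stop | 12 of 80 stop |
|---|---|---|
| Stoppers with an AE | 4 × 0.371 = 1.48 | 12 × 0.371 = 4.45 |
| Completers with an AE | 76 × 0.0051 = 0.39 | 68 × 0.0051 = 0.35 |
| Total | 1.87 | 4.80 |
| Percentage of 80 | 2.3% | 6.0% |
| Participants with ≥1 post-treatment day | 4 + 76 × 7/15 = 39.5 | 12 + 68 × 7/15 = 43.7 |
| Percentage of those | 4.7% | 11.0% |
| Post-treatment participant-years | (4 × 182 + 76 × 1.87)/365.25 = 2.38 | (12 × 182 + 68 × 1.87)/365.25 = 6.33 |
| Expected events per 100 participant-years | 100 | 100 |

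The ratio of crude percentages is 0.39. Restricting the denominator moves it only to 0.43. The rate per participant-year is equal in both arms, as it was set to be.

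**5. Sensitivity of the crude percentages.**
- 4 versus 8 stopping: 2.3% versus 4.2%.
- 4 versus 12, with both visits spread independently over their windows: 2.5% versus 6.1%.
- 4 versus 12, with half the stoppers followed and the rest contributing no post-treatment time: (2 × 0.371 + 0.39)/80 = 1.4% versus (6 × 0.371 + 0.35)/80 = 3.2%.

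**6. How much comes from stoppers.** At 2 or 4 AEs per participant-year, stoppers supply 77% to 92% of participants with a post-treatment AE when 10% to 20% stop and all are followed, and 62% to 84% if half are followed. When only 3% to 5% stop, the share is 31% to 69%. Their share of post-treatment time at 3% stopping is 53% to 69%.

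**The case against.** The strongest reply is that the SAP does not fix the denominator. SAP 4.5 names an analysis set, not the base of every percentage, and urinalysis sits under the same sentence while using participants with data. SAP 4.5.2 relies on the sponsor's core data standards and SAP 1 sends display details to the Output and Programming Specification, neither of which is available here. This stands in part: the Safety set is the default reading, not a stated rule, and the specification could set another base. It does not answer the absence of follow-up time, because step 4 shows that a better denominator alone barely helps.

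The illustration also assumes favourable inputs. A threefold imbalance in stopping has no support in the documents, and follow-up to Week 52 is only where possible. Participants who withdraw from the study may have little post-treatment time. This stands, and is why the size is given only as an illustration with a range.

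Finally, the tables are descriptive. No test of post-treatment AEs is planned, relative risks and risk differences are specified only for AEs of special interest, and the worst example above is about 2 versus 5 participants. This also stands and limits the importance of the point. The arms will still be shown side by side without the information needed to read them.

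**Conclusion.** The point holds as a small reporting weakness. The 28-day cut-off coincides with the nominal final visit, so crude post-treatment percentages depend on how many stop in each arm and how long they are followed. Under the assumptions in step 4 the artefact is 2.3% versus 6.0%; it shrinks with less follow-up or a smaller imbalance and vanishes if stopping and follow-up are alike in both arms.

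A reader might infer more than the documents support:
- That the tables mainly count who stopped treatment. This needs a stopping rate the documents do not give. It is so at about 10% or more, but not assured at 3% to 5%.
- That about half of completers have no post-treatment day. This assumes evenly used visit windows; on the nominal schedule it is all of them.
- That the SAP states the Safety set as the denominator, or that changing it cures the problem. It is a default, and the restricted percentages still differ (4.7% versus 11.0%).
- That a formal comparison between arms is compromised. None is planned for these tables.

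**What to change.** Add to SAP 4.5.2, for the post-treatment AE and SAE tables, three items by arm:
- the number of participants with follow-up beyond 28 days after the last dose
- total post-treatment participant-years, from that point to the end of each participant's AE collection
- events per 100 post-treatment participant-years

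Label the crude percentages as descriptive and not for comparison between arms, and state which denominator they use. The participant-years and rates are the essential part.

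The cost is SAP wording, one flag and one derived duration, with no change to trial conduct or data collection. The downside is imprecise rates: the illustration has only about 2.4 and 6.3 participant-years per arm. The rates also do not remove the selection in who stops, so the label should stay.

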#### **4.5.2.1. Adverse Events of Special Interest**

Adverse events of special interest (AESIs) are adverse events which are to be closely monitored as the development of mepolizumab progresses.

Systemic reactions are AESIs which are collected using targeted eCRF pages and further categorised by the investigator as either an allergic (type I hypersensitivity) or other systemic reaction. These events are required to be assessed against Sampson's diagnostic criteria for anaphylaxis [Sampson, 2006]. Local injection site reactions are also collected using targeted eCRF pages within the study.

AESIs of potential opportunistic infections, malignancies, serious cardiac, vascular and thromboembolic (CVT) events and serious ischemic events will be identified from a list of relevant preferred terms maintained within a project level reference dataset created based on the latest version of the MedDRA dictionary available at the time of source data lock for this study. Further details of how relevant preferred terms are identified for the AESIs are given in the OPS.

Separate summary tables showing the number and percent of participants with each type of AESI, broken down by preferred term will be created. These summaries will be reported as part of the standard AE/SAE tables for the AESIs of infections, serious infections, neoplasms, cardiac disorders and serious cardiac disorders. The relative risk and risk difference of each AESI between mepolizumab and placebo will be presented with 95% confidence intervals.

For each AESI a profile summary table will be produced containing information on event characteristics including, but not be limited to, the number of participants with the AESI, the number of occurrences of the AESI, the number of participants with a serious event or a drug related event, maximum severity, outcome and action taken.

Separate listings will be provided of participants with systemic reactions identified by the investigator as meeting the criteria for anaphylaxis, systemic reactions categorised as

allergic (type I hypersensitivity), systemic reactions categorised as other, and all other AESIs.

Summaries of AESIs will also be presented by Background INCS use subgroup (defined within Section 4.11.1).

